1 STUDY SUMMARY

1.1 Synopsis

Title:	ImpleMenting PhArmacogenetiC Testing in Gastrointestinal Cancers
Short Title:	IMPACT-GI
Study Description:	
Pharmacogenetic (PGx) variants in the DPYD and UGT1A1 genes are associated with fluoropyrimidines and irinotecan induced adverse events. However, testing for these variants is not routinely performed in clinical practice prior to the initiation of chemotherapy due to lack of a clinical assay with rapid turnaround time (TAT) and challenges in integrating genetic test results within the electronic health record (EHR). We hypothesize that providing clinicians with the ability to order rapid turnaround PGx test results along with specific dosing recommendations will increase the utilization of PGx tests to guide pharmacotherapy decisions and improve patient drug related outcomes. This is a non-randomized implementation study to determine the feasibility of establishing and integrating a PGx test into clinical care to guide chemotherapy in patients with gastrointestinal (GI) cancers. Effectiveness of the PGx-guided approach will be determined by comparing the incidence of severe treatment related adverse events to historical control group of GI cancer patients enrolled into the Penn Medicine Biobank (PMBB).

Objectives:	
Implementation Aims:
 
 1. To determine the feasibility of returning PGx results prior to the first dose of chemotherapy. 2. To determine the fidelity to the PGx guided dosing recommendations. 3. To determine the rate of testing among providers with patients eligible for testing 
Effectiveness Aims:
 
 4. To determine if providing PGx test results will decrease the number of patients severe treatment related events during the first six cycles of chemotherapy.

	
 5. To determine if providing PGx test results will improve patient reported outcomes (PRO) during the first six cycles of chemotherapy.
Primary Endpoint:	
 1. The proportion of PGx test results returned prior to the first dose of chemotherapy. [Time Frame: 14 days] 2. The proportion of dose modifications made in agreement with the genotype guided dosing recommendations at the first dose. [Time Frame: 14 days] 3. The proportion of tests ordered compared to the number of patient with eligible for testing. [Time Frame: 14 days]
Secondary Endpoints:	
 1. The proportion of patients experiencing severe treatment related adverse events (TRAEs) over the first six cycles of chemotherapy. [Time Frame: 6 cycles] 2. The relative dose intensity of 5-FU and irinotecan dosing over the first six cycles. [Time Frame: 6 cycles] 3. Patient reported outcomes (PROs) during the first six cycles of chemotherapy. [Time Frame: 6 cycles] 4. Patient knowledge about and attitudes towards PGx. [Time Frame: 6 months] 5. The incidence of patients of African ancestry experiencing TRAEs over the first six cycles of chemotherapy. [Time Frame: 6 cycles] 6. The frequency of actionable DPYD and UGT1A1 in various ancestry groups. [Time Frame: 6 months] 7. PFS and OS in patients after genotyping [Time Frame: 6 ± 2 months] 8. The costs of PGx-guided chemotherapy [Time Frame: 6 cycles]
Study Population:	
Inclusion criteria
 
 1. Male and female subjects, 18 years or older at time of study 2. Pathologically confirmed gastrointestinal malignancy for which treatment with a fluoropyrimidine and/or irinotecan is indicated 3. Able and willing to provide informed consent 4. Willing to undergo blood or saliva sampling for PGx testing and comply with all study-related procedures 5. Life expectancy of at least 6 months 
Exclusion criteria
 
 1. Prior treatment with irinotecan 2. DPYD or UGT1A1 genotype already known

	
 3. Severe renal or hepatic impairment (or unacceptable laboratory values) 4. Women who are pregnant or breast feeding, or subjects who refuse to use reliable contraceptive methods throughout the study 5. Treating physician does not want subject to participate
Phase:	N/a
Description of Sites/Facilities	
Penn Medicine sites:
 
 1. Perelman Center for Advanced Medicine (PCAM) 2. Penn Presbyterian Medical Center (PPMC) 3. Lancaster General Hospital (LGH)
Enrolling Participants:	Approximately 500-800 participants will be enrolled across the Penn Medicine sites.
Description of Study Intervention:	
Genetic: DPYD and UGT1A1 genotyping
 
The study utilizes a lab developed test (Center for Applied Genomics (CAG), Children's Hospital of Philadelphia, PA) performed in a Clinical Laboratory Improvement Amendments (CLIA) environment that provides identification of a patient's genotype determined from genomic DNA from a blood or saliva sample with a turnaround time of seven business days. The alleles identified and reported include DPYD*2A, *5, *6, *8, *9A, *10, *12, *13, rs2297595, rs115232898, rs67376798, HapB3 (rs75017182, rs56038477, rs56276561) and UGT1A1*6, *28.
 
This is a nonrandomized, prospective, open label study. Patients with gastrointestinal cancers that will be initiated on chemotherapy with 5-fluorouracil (5-FU), capecitabine, or irinotecan will be consented to undergo the PGx test. The PGx test order will be placed by the medical oncologist; a blood or saliva sample will be obtained by the phlebotomist and sent to CAG for genotyping. Results will be returned in the Precision Medicine tab in PennChart. For patients with an actionable genotype (variants that would require a dose adjustment of 5-FU, capecitabine or irinotecan), clinical decision support (CDS) tools will alert the ordering oncologist of the PGx result and the recommended dose adjustment. The prescribing oncologist will ultimately decide the chemotherapy dose incorporating clinical and/or genetic factors.

Study Duration:	2 years

[figure not shown]

Participant Duration:	6 months
------------------------------	----------

Key Roles and Study Governance

Sponsor University of Pennsylvania
Name, degree, title [name], MS Research Assistant Professor of Medicine Director, Pharmacogenomics, Penn Medicine Center for Genomic Medicine
Institution Name University of Pennsylvania Perelman School of Medicine Department of Medicine Division of Translational Medicine and Human Genetics
Address [name]
[contact]
Email [contact]

1.3 Schema

2 INTRODUCTION AND RATIONALE

2.1 Study Rationale

There are known pharmacogenetic (PGx) variants in the *DYPD* and *UGT1A1* genes associated with altered drug metabolism and prolonged drug exposure resulting in drug-related adverse events from fluoropyrimidine and irinotecan therapy. Testing for these variants is not performed in routine practice due to barriers in clinical implementation. These obstacles include a lack of rapid turnaround times of genotype results to impact clinical care, a lack of a standardized format for the return of test results in the electronic health record, inexperience of clinicians on interpreting and acting on PGx information, a limited number of prospective, randomized genotype-guided clinical outcomes trials, as well as cost considerations and reimbursement. We will conduct a non-randomized implementation study to determine the feasibility of establishing and integrating a PGx test into clinical care to guide chemotherapy in patients with gastrointestinal (GI) cancers. Effectiveness of the PGx guided approach will be determined by comparing the incidence of severe TRAEs to historical control group of GI cancer patients enrolled into the Penn Medicine Biobank (PMBB).

2.2 Background

Standard first-line systemic chemotherapy for most gastrointestinal malignancies consists of a fluoropyrimidine [intravenous 5-fluorouracil (5-FU) or oral capecitabine] in combination with irinotecan, oxaliplatin, and/or targeted agents. A unique subset of patients is at an increased risk of developing severe, chemotherapy-related adverse events from fluoropyrimidines and irinotecan due to germline variants in the *DYPD* (dihydropyrimidine dehydrogenase) and *UGT1A1* (uridine diphosphate-glucuronosyltransferase isoform 1A1) genes, respectively.

Up to 30% of patients develop severe fluoropyrimidine-related toxicity, such as diarrhea, hand-foot syndrome, mucositis, and myelosuppression at standard doses.¹ These events can be fatal in 1% of treated patients.¹ Similarly, as many as 20-35% of patients treated with irinotecan may experience severe toxicities, ranging from diarrhea to myelosuppression.² Given the life-threatening nature of severe adverse events, hospitalizations are often indicated which result in additional resource utilization costs. Subsequently, chemotherapy-related adverse events often lead to treatment delays or discontinuations that may impact tumor prognosis.

The *DYPD* gene encodes dihydropyrimidine dehydrogenase, or DPD, the metabolic enzyme responsible for the catabolism of 5-FU and capecitabine. A partial DPD enzyme deficiency is present about 3-5% of individuals of European ancestry while complete deficiency occurs less frequently at a rate of 0.2%.³ Four clinically relevant *DYPD* variants in European ancestry individuals and one clinically relevant *DYPD* variant in African ancestry individuals have been identified as resulting in a reduction of DPD enzyme activity of 25 to 50%.^{1,3-5} These variants

include *2A (c.1905+1G>A, rs3918290), *13 (c.1679T>G, rs55886062), c.2846A>T (rs67376798), and HapB3 (c.1129-5923C>G, rs75017182; c.1236G>A, rs56038477), and c.557A>G (rs115232898). Genetic variants associated with reduced UGT1A1 enzyme activity include *UGT1A1**28 (rs8175347), *6 (rs4148323) (Table 1).^{6,7}

Table 1. Actionable pharmacogenetic variants impacting response to chemotherapy

Gene	Variant				MAF		Allele Function ^{1,6}
	Haplotype	Nucleotide change	Protein change	rsID	EA	AA	
DPYD	*2A	c.1905+1G>A	-	rs3918290	0.008	0.003	No function
	*8	c.703C>T	R235W	rs1801266	0.0001	NR	No function
	*10	c.2983G>T	V995F	rs1801268	NR	NR	No function
	*12	c.1156G>T	E386X	rs78060119	NR	NR	No function
	*13	c.1679T>G	I560S	rs55886062	0.001	0.000	No function
	HapB3	c.1236G>A	E412E	rs56038477	0.024	0.003	Decreased function
		c. 1129-5923C>G	-	rs75017182			Decreased function
		c.483+18G>A	-	rs56276561			Decreased function
		c.557A>G	Y186C	rs115232898	0.0001	0.012	Decreased function
		c.2846A>T	D949V	rs67376798	0.004	0.003	Decreased function
UGT1A1	*6	c.211G>A	G71R	rs4148323	0.008	0.004	Decreased function
	*28	c.-41_-40dupTA(TA ₇)	-	rs8175347	0.316	0.373	Decreased function

MAF minor allele frequency, EA European ancestry, AA African ancestry

The NIH-funded Clinical Pharmacogenetics Implementation Consortium, which issues evidence-based peer-reviewed guidelines on clinically actionable PGx variants, recommends a 50% dose reduction in individuals with one reduced function allele (intermediate metabolizers) and avoidance of therapy in those with two reduced function alleles (poor metabolizers).¹ Recent studies have shown that preemptive genotyping for *DPYD* variants can significantly reduce drug-related adverse events and improve patient safety.⁸⁻¹⁰ In a 2018 multicenter European study, Henricks et al. demonstrated the feasibility of prospective genotype-guided fluoropyrimidine dosing in clinical practice. When comparing the safety outcomes in dose-reduced variant carriers to a historical control given the standard dose, severe toxicity was found to be higher in the standard dose population (39% vs. 23%, p=0.0013).⁹ A study conducted by Kleinjan et al. in 2019 further supports the practice of *DPYD* genotype-guided dosing, demonstrating that performing initial dose reductions of capecitabine in heterozygous *DPYD* variant carriers followed by tolerance-based dose escalation did not lead to higher toxicity compared to patients of wild-type status (37.9% vs. 27.3%, p=0.54).¹⁰ There are few studies directly investigating the decreased function c.557A>G variant with evidence currently limited to case reports.⁵

The FDA drug labeling for irinotecan recommends approximately a 20-40% reduction in the starting dose in *UGT1A1* *28/*28 homozygous individuals (poor metabolizers) to avoid hematological toxicity.¹¹ The Dutch Pharmacogenetics Working Group from the Royal Dutch Pharmacists Association recommends an initial dose reduction of 30% in poor metabolizers, with subsequent dose escalation guided by patient tolerance and neutrophil counts.¹² A 2007 meta-analysis by Hoskins et al. evaluating a variety of irinotecan-containing regimens found that

*UGT1A1**28 genotyping would be likely to improve rates of severe neutropenia in homozygous patients given high doses of irinotecan ($>250 \text{ mg/m}^2$) (OR 27.8, $p=0.05$).¹³ A subsequent 2010 meta-analysis by Hu et al. reported that the same genotype was also associated with an increased risk of neutropenia at doses of 150 mg/m^2 to 250 mg/m^2 (RR 2.0, $p<0.01$) and at lower doses ($<150 \text{ mg/m}^2$) (RR 2.4, $p<0.01$).¹⁴

DYPD genotyping has suboptimal sensitivity and positive predictive value (PPV), because DPD activity is also impacted at the post-transcriptional level, thus alternative methods have been proposed to identify those at risk for fluoropyrimidine-associated toxicity.¹⁵ Measuring DPD activity is one option, but it is technically and logistically challenging to perform in a clinical setting.¹⁶ Another method that is being investigated is the measurement of pre-treatment uracil.¹⁵ DPD converts its endogenous substrate uracil into dihydrouracil (DHU). In one study, pre-treatment uracil was found to be superior to the DHU/uracil ratio as a predictor of severe toxicity and high pre-treatment uracil concentrations were strongly associated with overall severe toxicity (odds ratio 5.3, $p=0.009$) severe GI toxicity (OR 33.7, $p<0.0001$), toxicity related hospitalization (OR 16.9, $p<0.0001$), and fatal treatment-related toxicity (OR 44.8, $p=0.001$).¹⁵ In addition, genotyping *DYPD* variants together with the assessment of uracil concentrations improved the predictive accuracy of fluoropyrimidine associated toxicity. This study was done in a European population and the dynamic range of uracil needs to be confirm in a more ethnically diverse population as seen within Penn Medicine. Within the current study we will collect a pretreatment plasma sample to retrospectively examine the association of uracil concentrations with fluoropyrimidine associated toxicity within our patient population.

2.2.1 *Description of intervention*

The study utilizes a laboratory developed test for PGx variants in *DYPD* and *UGT1A1*, performed in a CLIA environment and provides identification of a patient's genotype determined from genomic DNA from a blood or saliva sample (See Section 6.6.1 Study Intervention Description and Appendix 14.5 Validation Reports).

3 STUDY OBJECTIVES AND ENDPOINTS

Hypothesis:

Providing clinicians with the ability to order a PGx test with a rapid turnaround time for results, along with specific dosing recommendations, will increase the utilization of PGx tests to guide pharmacotherapy decisions and improve patient drug related outcomes.

OBJECTIVES	ENDPOINTS
Primary	

 1. To determine the feasibility of returning PGx results prior to the first dose of chemotherapy 2. To determine the fidelity to the PGx guided dosing recommendations. 3. To determine the rate of testing among providers with patients eligible for testing 	
 1. The proportion of tests returned prior to the first determined dose of chemotherapy. 2. The proportion of dose modifications made in agreement with the genotype guided dosing recommendations at the first dose. 3. The proportion of tests ordered compared to the number eligible for testing.
Secondary	

 1. To determine if providing PGx test results will decrease the number of patients experiencing severe treatment related adverse event (TRAEs) during the first six cycles of chemotherapy. 2. To determine the relative dose intensity of 5-FU and irinotecan administered to each patient over the first six cycles. 3. To determine if providing PGx test results will improve patient reported outcomes (PRO) during the first cycles of chemotherapy. 4. To assess patient attitudes towards PGx. 	
 1. The proportion of patients severe TRAEs during the first six cycles of chemotherapy. 2. The relative dose intensity will be calculated as the cumulative administered dose divided by the anticipated cumulative dose over six cycles reported as mg/m² 3. Patient reported outcomes (PROs) during the first six cycles of chemotherapy as assessed on a Likert scale. 4. Patient knowledge about and attitudes towards PGx testing as assessed on a Likert scale.
Tertiary	

 1. To determine if chemotherapy-induced toxicity differs by ancestry group. 2. To determine the frequency of actionable DPYD and UGT1A1 in various ancestry groups. 3. To determine if PGx testing influences progression-free (PFS) and overall survival (OS). 4. To determine the cost-effectiveness of PGx guided chemotherapy dosing. 5. To determine the association of pre-treatment plasma uracil concentrations with severe (Grade 3 to 5) fluoropyrimidine induced toxicity with the first dose. 	
 1. The proportion of patients experiencing a serious treatment relate adverse event during the first six cycles of chemotherapy stratified by self-reported ancestry. 2. Minor allele frequency of variants in DPYD and UGT1A1 reported by self-reported ancestry. 3. PFS and OS in patients at 6 ± 2 months. 4. Means and variances of cost in the genotype-guided group as compared to the historical control group (Costs of hospitalizations, treatment, PGx test, medical services) 5. Pre-treatment plasma uracil concentrations as measured by HPLC.

OBJECTIVES	ENDPOINTS
Optional Microbiome Substudy at PCAM only	
1. To determine whether the microbiome composition impacts the occurrence of chemotherapy-induced adverse events	1. The change in bacterial abundance as measured by operational taxonomic units (OTUs) 2. The change in bacterial composition or beta diversity as measured by weighted UniFrac distance

4 STUDY PLAN

4.1 Study Design

This is a non-randomized, prospective, open-label implementation study to determine the feasibility of establishing and integrating a PGx test into clinical care. The effectiveness aims will be assessed by comparing toxicity outcomes using a historical control group without clinical genotyping. The implementation will be deployed across cancer care sites within Penn medicine in sequential fashion, starting with PCAM followed by PPMC, and LGH.

Patients with a GI malignancy initiating chemotherapy with a fluoropyrimidine (5-FU or capecitabine) and/or irinotecan will be consented to undergo *DYPD* and *UGT1A1* genotyping, the study intervention. The PGx test order will be placed by the research coordinator and signed by the medical oncologist; a blood sample will be obtained by the phlebotomist, or saliva self-collected by the patient in clinic, and sent to CAG for genotyping. Results will be returned in the Precision Medicine tab in PennChart. For patients with an actionable genotype (variants that would require a dose adjustment of 5-FU, capecitabine or irinotecan), clinical decision support (CDS) tools will alert the ordering oncologist of the PGx result and the recommended dose adjustment. The prescribing oncologist will ultimately decide the chemotherapy dose incorporating clinical and genetic factors. The efficacy and safety of this PGx-guided approach will be determined by comparing the incidence of severe treatment related adverse events to a historical control group of GI cancer patients enrolled into PMBB.

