5 STUDY POPULATION AND DURATION OF PARTICIPATION

5.1 Inclusion Criteria

In order to be eligible to participate in this study, an individual must meet all of the following criteria:

1. Able and willing to provide informed consent
2. Male or female, aged 18 years or older at the time of study initiation
3. Pathologically confirmed gastrointestinal malignancy for which treatment with a fluoropyrimidine and/or irinotecan is indicated
4. Willing to undergo blood or saliva sampling for PGx testing and comply with all study-related procedures
5. Life expectancy of at least 6 months

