5.2 Exclusion Criteria

An individual who meets any of the following criteria will be excluded from participation in this study:

Exclusion criteria

1. Prior treatment with irinotecan
2. *DPYD* or *UGT1A1* genotype already known
3. Severe renal or hepatic impairment (or unacceptable laboratory values), including:
 - Neutrophil count of $<1.5 \times 10^9/L$, platelet count of $<100 \times 10^9/L$
 - Hepatic function as defined by serum bilirubin $>1.5 \times$ upper limit of normal (ULN), alanine aminotransferase (ALT), and aspartate aminotransferase (AST) $>2.5 \times$ ULN, or in case of liver metastases ALT and AST $>5 \times$ ULN
 - Renal function as defined by serum creatinine $>1.5 \times$ ULN, or creatinine clearance $<60 \text{ ml/min}$ (by Cockcroft-Gault Equation)
4. Women who are pregnant or breast feeding, or subjects who refuse to use reliable contraceptive methods throughout the study
5. Treating physician does not want subject to participate

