7.5 Data collection at each chemotherapy infusion (time 0 to 6 cycles)

The following information will be assessed at each chemotherapy visit by study personnel or extracted from the medical record with each chemotherapy treatment during the first six cycles if performed as part of usual care and available in the medical record.

- Routine physical examination: height (cm), weight (kg), calculated body mass index (BMI)
- Vital signs: heart rate, blood pressure
- Hematology: hemoglobin, hematocrit, white blood cell count, ANC, neutrophils, eosinophils, basophils, lymphocytes, monocytes, platelets prior to treatment
- Clinical chemistry: sodium, potassium, calcium, glucose, creatinine, BUN, AST, ALT, alkaline phosphatase, total bilirubin, albumin
- Creatinine clearance (using Cockcroft-Gault formula)
- Concomitant medications (including start date, dose, unit, frequency, route of administration and indication)
- Chemotherapy course: dates of treatment, dose of each treatment for first 6 cycles
- Adverse events: date of reported treatment-related symptoms, date of emergency department (ED) visits and/or hospitalizations (if applicable), clinical course and symptom duration, ED/hospitalization medical billing information. Severe TRAEs are defined as those requiring treatment in the hospital, ED, or Oncology Evaluation Center (OEC).
- Serial questionnaires assessing patient reported outcomes (PROs) for symptoms associated with adverse events will be prospectively collected by the study team at the time of each treatment for the first 6 cycles (see data collection tool in Appendix 14.6)

The following information will be extracted from the medical records and/or tumor registry at the 6-month (\pm 2 months) follow-up period if performed as part of usual care and recorded in the medical record.

- Overall patient survival (duration of patient survival from time of treatment initiation)
- Progression free survival (time from treatment initiation until disease progression or worsening)
- Information regarding tumor response from computed tomography (CT) scans will also be collected as available. This is expected to be classified by the treating oncologist as complete response (CR), partial response (PR), stable disease (SD), or progressive

disease (PD) per response evaluation criteria in solid tumors (RECIST) guideline version 1.1.

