8 STATISTICAL PLAN

8.1 Sample size

For the implementation aims, the sample size is based on average GI oncology clinical volume and anticipated number of patients that are eligible for testing. We anticipated testing 500-800 patients during the course of the study at the three Penn Medicine sites. No hypothesis testing will be performed.

For the effectiveness aims, we hypothesize that the chemotherapy-related severe TRAEs will decrease from 60% in the variant carriers receiving full dose chemotherapy in the historical control group enrolled into the PMBB to 30% in variant carriers receiving genotype guided chemotherapy.¹⁸ The following table presents the power for different sample sizes per group and different expected proportions experiencing severe TRAEs in the PGx group, based on two-sided Fisher's exact test at the alpha level of 0.05 (Table 5). Based on the frequencies of *DPYD* and/or *UGT1A1* in the population (~10%), testing 500 patients in each group will result in ~50 patients with actionable genotypes.

Table 5. Power estimate for the reduction in Severe TRAEs with PGx testing

Toxicity rate	39% in PGx	35% in PGx	30% in PGx
N in each group with actionable variants			
18	17.8%	24.8%	35.6%
36	32.3%	45.8%	63.6%
48			80%
54	49.4%	66.3%	83.9%
70		80%	
72	67.4%	82.9%	
97	80%		

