We will obtain data from Data Analytics Center (DAC) on service utilization and costs. These will include: number of physician visits; number of emergency department visits; number of hospitalizations; length of hospital stay; number of emergency department and hospital admissions associated with drug-related adverse events; DPYD and UGT1A1

genetic testing costs; physician visit cost; emergency department visit costs; hospitalization costs; inpatient and physician-administered medication costs; and total costs. Care Everywhere will be utilized to obtain information if patients received care outside Penn Medicine. Additionally, medical records will be requested for admissions that occur outside of Penn Medicine.

We will compare utilization and costs incurred by the PMBB usual care group with utilization and costs incurred by the PGx group using Poisson regression methods (for number of visits), and linear regression methods with appropriate transformations (e.g., log-transform, winsorization) to account for skewness in utilization and cost distributions.

4. Survival Analysis

Overall survival and progression free survival at approximately six months will be compared between the PMBB historical control group vs. the PGx group by use of Kaplan-Meier estimators and log-rank tests. Cox proportional regression analysis will be performed to adjust for clinical covariates including age, sex, race, tumor type, cancer stage, BMI, and ECOG performance status.

5. Pre-treatment uracil and fluoropyrimidine associated toxicity

First, we will examine the range of pre-treatment uracil concentrations with the association of severe toxicity to determine if there is a cut-off whereby toxicity occurs. Previous studies have proposed uracil $> 16\text{g/ml}$ as highly predictive for severe toxicity, but we will validate this cut-off in our patient population.¹⁵ We will also examine whether the pre-treatment uracil levels vary in *DPYD* variant carriers. Second, we use logistic regression models to determine the risk of severe toxicity including a binary factor for uracil concentration (above and below cut-off), with adjustment for age, sex and treatment regimen.

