10.2 Risk/Benefit Assessment

10.2.1 Known Potential Risks

Blood will be drawn from all participating patients for determining the genotype prior to start of chemotherapy. Risks of venipuncture include possible bruising, infection at the site, and in rare cases, fainting. These risks are minimized by using trained personnel. The impact on clinical oncologic outcomes is unknown. Chemotherapy dose adjustments will be performed by the treating oncologist according to his or her clinical judgment.

There can also be a risk in knowing genetic information. New health information about inherited traits that may affect participating patients and or their blood relatives may be found during the research study. DPD deficiency is an autosomal recessive disease; carriers usually do not have related health problems, but they do have an increased risk of complications when treated with fluoropyrimidine therapy.²³ *UGT1A1* plays a role in the metabolism of bilirubin and is associated with hereditary hyperbilirubinemia syndromes. The *28 variant is a common cause of Gilbert syndrome.⁶ Individuals with Gilbert syndrome may experience transient elevations in unconjugated plasma bilirubin in response to various triggers (e.g., fasting, infection, or medications). Genotypes most implicated in Gilbert syndrome are *UGT1A1**28/*28 and *UGT1A1**6/*6. Crigler-Najjar syndrome type I is very rare and results from deleterious

UGT1A1 mutations that results in hyperbilirubinemia and occur early in childhood therefore the PGx testing is unlikely to result in incidental findings. However, identification of a heterozygous state may have implications for prenatal genetic counseling. The treating oncologist may choose to return these incidental findings if pertinent for clinical care. For the purposes of this current study, variants in the *UGT1A1* gene will be interpreted to guide irinotecan drug dosing.²⁴

Additionally, there is the risk of loss of privacy with storing the health and genetic data of participating patients. Very rarely health or genetic information could be misused by employers or insurance companies; however, in such events, patients may have difficulty finding or maintaining a job or insurance. Laws such as the federal Genetic Information Non-Discrimination Act (GINA) prohibit employers and health insurers from discriminating against individuals based on their genetic information. However, GINA does not protect against life insurance or long-term care insurance.

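### The plan states no eligibility, index-date or consent-timing rule for the PMBB historical controls, and the TRAE comparison with them is unadjusted

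*Combined protocol and SAP*

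**What the plan says.** **Controls.** Protocol 4.1 describes a "historical control group of GI cancer patients enrolled into PMBB" and says toxicity will be assessed "using a historical control group without clinical genotyping". Section 8.1 expects severe TRAEs to "decrease from 60% in the variant carriers receiving full dose chemotherapy in the historical control group enrolled into the PMBB to 30% in variant carriers" under genotype-guided dosing. The cost paragraph of section 8.2 refers to "utilization and costs incurred by the PMBB usual care group". SAP item 27 compares the cohorts within DPYD variant carriers and within UGT1A1 poor metabolizers.

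**Prospective patients.** Section 5.1 requires "Life expectancy of at least 6 months". Section 5.2 excludes prior irinotecan and sets neutrophil, platelet, liver and kidney limits. One of these is "Hepatic function as defined by serum bilirubin" above 1.5 times the upper limit of normal. SAP item 18 removes participants who were tested after chemotherapy or who did not receive a qualifying agent.

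**Analysis.** Protocol 8.2.2 compares severe TRAEs between cohorts by Fisher's exact test, and SAP item 27 by chi-square. Neither adjusts for covariates. The protocol adjusts RDI by linear regression, but the SAP uses t-tests. The SAP's multivariable TRAE model lists no cohort term. Survival in section 7.5 is the "duration of patient survival from time of treatment initiation", within a list of data to be collected on trial participants.

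**The concern.** The effectiveness question depends on whether the control event rate is what the prospective patients would have had without testing. The plan's descriptors for controls cover disease, biobank membership, treatment and genotype. They do not cover fitness at first dose or the point from which a control is under observation. Followed literally, the plan compares a cohort restricted by eligibility with one that is not, using tests that cannot correct for the difference.

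Two mechanisms pull in opposite directions. Controls who could not have entered the trial (poor marrow, liver or kidney function, or prior irinotecan) could raise the control event rate and make PGx dosing look safer. Controls who joined the biobank after starting chemotherapy had to survive until they joined. That would flatter control survival and might lower the control event rate. Nothing suggests that the two cancel.

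The bilirubin limit needs separate mention. Section 10.2.1 says that the \*28 "variant is a common cause of Gilbert syndrome", and section 14.4.1 ties reduced UGT1A1 activity to raised SN-38, raised bilirubin and dose-limiting toxicity. A limit applied to one cohort only may therefore change the case mix in the UGT1A1 poor-metabolizer comparison.

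**Working it through.** **1. The rules side by side.**

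| Rule | Prospective cohort | PMBB controls |
|---|---|---|
| GI cancer | 5.1 | 4.1 |
| Fluoropyrimidine and/or irinotecan | 5.1; SAP item 18 | Chemotherapy implied by 8.1; no entry rule |
| No prior irinotecan | 5.2 | Not stated |
| Blood count, liver and kidney limits | 5.2 | Not stated |
| Life expectancy of 6 months | 5.1 | Not stated |
| Under observation before first dose | 7.1; SAP item 18 | Not stated; the test-timing exclusion cannot operate in untested patients |
| Index date | Treatment initiation for survival (7.5) | Not stated |

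**2. The plan's own power figure.** Inputs from section 8.1 are 60% versus 30%, 48 carriers per group, and a two-sided Fisher's exact test at 0.05. Power is the sum, over all pairs (a, b) with Fisher p ≤ 0.05, of Bin(a; 48, 0.60) × Bin(b; 48, 0.30). The result is 80.0%, as in Table 5. All 14 filled cells of Table 5 reproduce to within 2 points. The arithmetic is sound; what is unsecured is whether the 60% refers to comparable patients.

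**3. Sensitivity to a non-comparable control rate (assumed shifts).** Assume no true effect, a 30% rate in the PGx group, 50 carriers per group and the same Fisher test.

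| Control rate | 15% | 20% | 25% | 30% | 35% | 40% | 45% | 50% |
|---|---|---|---|---|---|---|---|---|
| Rejection | 35% | 16% | 5.8% | 3.1% | 5.5% | 13% | 27% | 46% |

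To connect the shifts to eligibility, suppose a share q of controls would have been ineligible and has event rate r, with the rest at 30%. The control rate is (1 − q) × 0.30 + q × r.
- q = 20%, r = 60%: 0.24 + 0.12 = 36%; rejection 6.5%.
- q = 20%, r = 75%: 0.24 + 0.15 = 39%; rejection 11%.
- q = 40%, r = 60%: 0.18 + 0.24 = 42%; rejection 18%.
- q = 40%, r = 75%: 0.18 + 0.30 = 48%; rejection 38%.

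**4. Late biobank consent and survival (assumed).** Take exponential survival with S(6 months) = 0.85 and consent uniform over months 0–6. The hazard is λ = −ln(0.85)/6. The chance of being alive at consent is (1 − 0.85)/(6λ) = 0.923. Apparent six-month survival is 0.85/0.923 = 92.1%. If only half of controls join late, it is 0.85/(0.5 + 0.5 × 0.923) = 88.4%.

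**5. Late consent and TRAE, through death alone.** Section 2.2 says fluoropyrimidine toxicity can be fatal in 1% of treated patients. If that applied to carriers and every such death were lost, 60% would become (0.60 − 0.01)/0.99 = 59.6%. If the 7.7% lost in step 4 (1 − 0.923) all had severe TRAEs, it would become (0.60 − 0.077)/0.923 = 56.7%. Survival is therefore much more exposed to this mechanism than TRAE.

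**The case against.** The strongest reply is that silence is not evidence of a flaw. The documents do not say how controls were screened or when they consented, so the investigators may have applied suitable rules. That stands against a stronger reading: a reader might infer that the cohorts are different risk sets, and the documents do not show this. They show only that sameness is neither required nor verifiable. The controls are also not described by disease and biobank membership alone. Treatment, absence of clinical genotyping and restriction by genotype are stated, though none of these is an eligibility or timing rule.

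A reader might infer from section 7.5 that the control clock starts at treatment initiation. That section concerns participants' data, so the index date for controls is simply absent.

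A reader might also infer that the bilirubin limit removes UGT1A1 poor metabolizers from the prospective cohort in some known proportion. Section 10.2.1 speaks only of possible transient elevations, and no passage says how many patients exceed the limit. Since the SAP compares cohorts within poor metabolizers, a smaller share of them would not itself bias the contrast. A changed case mix among those who remain could. Any effect of the limit on reported allele frequencies involves no controls and is no part of this point.

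Some protection is already planned. Baseline characteristics are to be compared, and the protocol adjusts RDI and Cox survival for several covariates. But a baseline comparison describes imbalance without removing it, and the SAP replaces the RDI regression with t-tests. The TRAE contrast is unadjusted in both documents. The SAP lists no cost comparison, and for survival only that one-year figures were reported, so exposure there is narrower than the protocol suggests.

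**Conclusion.** The concern holds in this form: the plan states no eligibility, index-date or consent-timing rule for the PMBB controls, while prospective patients face both eligibility limits and a pre-chemotherapy testing rule. The unadjusted TRAE comparison, and the SAP's unadjusted RDI comparison, cannot make up the difference. Comparability is not secured and the direction of bias is unknown.

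No single size can be given, because the documents report neither the share of ineligible controls nor the timing of PMBB consent. Every figure in steps 3 to 5 rests on assumed values. They show that a 10-point error in the control rate would be enough to raise false rejection about four- to five-fold, and that late consent would distort survival more than TRAE. The effect of the one-sided bilirubin limit cannot be estimated. Feasibility, which uses the prospective arm only, is untouched.

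**What to change.** 1. In protocol 4.1 and SAP item 18, restrict controls to GI cancer patients starting a fluoropyrimidine and/or irinotecan who meet the chart-verifiable 5.1–5.2 criteria at first dose: no prior irinotecan, and the same neutrophil, platelet, bilirubin, transaminase and renal limits where recorded. Report how many controls each rule removes and how many lack the value. Life expectancy cannot be checked in retrospect, so name it as a remaining difference.
2. Set first dose as the index date for controls.
3. Left-truncate survival at biobank consent, or require consent by first dose. Run a TRAE and RDI sensitivity analysis excluding controls who consented after first dose.
4. State that the bilirubin limit may change the case mix of the UGT1A1 poor-metabolizer comparison if it cannot be applied to controls.

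**Cost.** The control group shrinks. With 48 PGx carriers and 60% versus 30%, losing 20% of 48 control carriers (38 left) lowers Fisher power from 80% to 75%; losing 40% (29 left) lowers it to 70%. Control laboratory values and consent dates may have to be extracted, since the documents do not say that they were. SAP item 14 places the analyses in May–June 2024, so this means a rerun as well as new wording. If controls were in fact screened this way, stating the rules and the counts is enough.
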